Prevention and Treatment Services (CHIPTS; [name] PI) where he works with a team of colleagues to develop funded research on application of the next generation of technological advances and biomedical approaches to prevent HIV transmission.

The charge of the DSMB includes advising the multi-PIs on study procedures related to risk to subjects, consideration of the interim results from the study, and providing reports to the IRBs at USC and RTI International as requested from this bodies. No members of the board have any conflicts of interest with the study or its key personnel. Members will meet at least annually. In the event that a serious adverse event occurs, the DSMB will be notified of the event within 10 days and convened within a month to review the case. The multiple PIs acknowledge the requirement to provide a report on DSMB activities in the annual progress report to NIDA.

9.0 CLINICAL AND LABORATORY EVALUATIONS AND STUDY CALENDAR

Not applicable

10.0 CRITERIA FOR EVALUATION AND ENDPOINT DEFINITIONS

NOT APPLICABLE

11.0 SPECIAL INSTRUCTIONS:

NOT APPLICALBE.

12.0 DATA COLLECTION AND MONITORING

Data Security. On all data records, participants will be identified by unique ID numbers rather than names. Forms containing participants' names (release of information, and consent form) will be kept in separate and locked file cabinets. The tracking database, containing participants' names and contact information will be kept in a password protected database on an encrypted laptop that is backed up nightly to a server at each of the study sites (USC and RTI). Both the forms and the database will be, accessible only to the Study Coordinators, Project Director and Principal Investigators.

Data Storage. The data will be stored as follows:

Informed consent	Locked file cabinet (Study Coordinator, Project Director and Principal Investigators will have access).
Release forms	Locked file cabinet with informed consent. (Study Coordinator, Project Director and Principal Investigators will have access)
Tracking database (computerized)	Locked file cabinet (Study Coordinator, Project Director and Principal Investigator will have access).
Biometric Information database (computerized)	On Study Coordinator's laptop, used in office and at field site. Laptop will be encrypted and files will be password protected and backed up to an FTP secure server at RTI at the end of each day.
Interview data – Screener, 6 and 12 month follow-up (computerized)	On field laptops. Encrypted and password protected. Data will be uploaded to an FTP site at RTI at the end of each day and automatically deleted from laptops.

Paper forms and databases containing identifying information will be destroyed within 30 days of the completion of the study.

Data transfer will occur through the use of password protected USB jump drives. Completed interviews will be copied and pasted into the USB storage device. These devices will then be immediately transported to USC or RTI where they will be downloaded onto a secure computer. Data files on field site computers will be deleted and the recycling bin emptied. One advantage of using the Questionnaire Development System for data collection and transfer is that in the unlikely event that interview computers are stolen or the USB storage device is misplaced, the actual data files cannot be viewed without a data warehouse module. The data warehouse module will not be installed on computers used for the collection of data or on the USB device. Once data is stored on USC/RTI computers, these computers will be maintained in secured, password-protected folders, accessible only to designated staff through the USC file server. The surveys will be securely downloaded and maintained in the database of [name]. Drs. [name] and [name] have successfully used similar methods for data management in other multisite NIDA-funded studies.

Elucidation data will consist of pen and paper survey forms for Study 1 and digitally recorded, qualitative interviews for Study 2. Study 1 forms will contain no identifying information and limited demographic information (sex, race, age). After data has been entered into a data entry form, paper versions of the survey will be destroyed. Study 2 will only include identification number on recording. Participants will be asked to use a fake name to refer to themselves and others in the recording. This has worked well in the past. No information will be collected that connects an individual by name to the audio recording. Following transcription, audio files will be deleted for audio-recorders and study computers.

13.0 STATISTICAL CONSIDERATIONS

13.1. Data analysis will involve (a) understanding the structure of all of the variables, (b) assessing whether randomization worked, (c) assessing and addressing intervention fidelity, and (d) testing the three hypotheses proposed in Aims 1, 2, and 3. First, we will employ exploratory data analytic techniques using the survey data collected at baseline and the 6- and 12-month follow-up. Dispersion and central tendency measures (e.g., means, standard deviations, medians, proportions) will be calculated for all items. The distributional properties and reliability of continuously scaled variables will be examined. We will also create longitudinal plots to identify trends in the key variables. We will also assess whether there is any statistically significant differential loss to follow-up between the two conditions. Any variable that is statistically significantly associated with loss to follow-up between conditions will also be included as a covariate in the hypothesis testing analyses. Next, we will examine fidelity to ensure compliance to the intervention based on observed intervention check lists that document the receipt of the intervention as manualized, compared with any changes that may occur. We can treat fidelity in the model as parameterized as a covariate in the observed model. Finally, we will test the three hypotheses. Similar procedures will be used to determine if the sex risk reduction intervention was efficacious.

Aim 1: To test the efficacy of CTC on reducing the number of non-injectors initiated into injection (counts) by PWID. Hypothesis 1(H1): PWID who receive CTC will report initiating fewer non-injectors into drug injection at 6 and 12 months as compared with PWID in the equal attention control condition. To test H1, we will conduct structural equation modeling (SEM) using Mplus (release 7.11).99 Our primary outcome analysis is based on an outcome that is distributed as counts of the number of episodes initiating someone into drug injection. This is a standard Poisson count variable with a potential inflation of the number of zeros as there will likely be many who do not initiate others (e.g., zero-inflation). This Poisson count outcome can essentially be thought of as consisting of two separate, yet interrelated, processes-one in which the participant engaged in the behavior of initiating someone else at all (i.e., binary yes/no) and another in which we assess the number of times the participant initiated someone (ranging from 1 to j, where j=the number of episodes initiating someone. In SEM literature, this is referred to as a two-part process for zero inflated Poisson, as SEM models these two processes separately as unique latent processes.¹⁰⁰ As this outcome is collected as part of an intervention with a baseline (T0) and two follow-ups (T1, T2), the model is parameterized to accommodate three time points, following Olsen and Schafer (2001).¹⁰⁰ Note that with three time points, the implied model is mis-identified given the number of measured variables in the variance-covariance from the observed data in an SEM measurement model with an intercept (i) and slope (s) for 3 observations.¹⁰¹⁻¹⁰³ However, joint modeling the ZIP as a two-part process redresses the identification problem, and results in 6 measured variables, one for the process in which the participant actually initiated another person (0 for no, 1 for yes) and another for the

change/reduction in the number of initiations over the 3 observation times (1 to i). The first part of the analysis will involve characterization of the measurement model for the change over time from T0 to T1 and from T1 to T2. As shown in Figure 3, the model will include a treatment covariate representing the effect of the CTC intervention on changes over time for the binary (sU) and count (sZ) latent variables, and it may contain other covariates identified as having been distributed differentially by condition at baseline or associated with loss to follow-up. Note that if there are no differences at baseline in preliminary bivariate analyses, there is no need to include a treatment effect on the intercept for the SEM because with no differences at baseline, the intercept test for difference is likely to be non-significant so there is no value in risking the extra degrees of freedom. Through model constraints, we will also examine specific differences between conditions within time points (e.g., T1 or T2) and between time points (e.g., change over time from T0 to

Figure 3. Two-Part Zero-Inflated Poisson SEM

T1). There will be little need for additional covariates to control for potential inflation of the correlations due to recruitment sites, as the targeted sampling will ensure full coverage across the locations where PWID congregate in LA and SF. We will, however, explore differences between the two sites, and may introduce a control variable to account for large-scale environmental differences between the two sites. To avoid any analytic decisions being driven by a desire for a certain result, the statistician and data analysis team will be blinded as to whether 0 or 1 denotes the treatment or control condition until the analyses are completed. There is also potential for contamination, which we will assess by asking the respondents in the control condition their level of exposure to intervention components, as described in Section 3.5.17.3. We will follow procedures outlined by Keogh-Brown et al. (2007) using complier average causal models (CACE),¹⁰⁴ in which the bias associated with contamination is significantly reduced by averaging the estimated causal effect over classes of participants that differ in the level of exposure to contamination. Each person in the control group will be assigned to a class, depending on their level of exposure and type of exposure, using latent classification techniques utilized by [name] in previous publications.¹⁰⁵ Lastly, we will compare differences in examining the rate of change versus the standardized difference at each follow-up point (e.g., compare counts of injection initiation at 6m and 12m) and test for differences by condition. The latent change model has more power than the raw difference approach, and we will present differences in our published work if the outcome is sensitive to model estimation.

Aim 2: To test the efficacy of CTC on reducing the number of times PWID are asked to initiate (counts) someone into injection. H2: PWID who receive CTC will report having been asked fewer times to initiate someone into drug injection at 6 and 12 months as compared with PWID in the equal attention control condition. This model will be estimated in the same manner as the model for the outcome of the actual number of reported counts, save that this one will estimated using the self-reported counts by the respondent regarding being asked to initiate another person.

Aim 3: To test whether injection initiation social learning risks (injecting in front of, describing injection to, and speaking positively about injection to non-injectors) act as mediational mechanisms for the efficacy of the CTC intervention on initiation and request-to-initiate outcomes. H3: Social learning variables will significantly mediate the association between the CTC intervention and episodes of initiating and being requested to initiate someone into drug injection at 6 and 12 months. The outcome variable will remain counts of the number of episodes initiating someone into drug injection (Aim 1) and the counts of request to initiate another person (Aim 2). The mediational models will be specified following the work of Baron and Kenny and newer generalizations.¹⁰⁶⁻¹⁰⁸ With only three time points, we can examine the effect of baseline randomization to treatment status on 12-month counts of injection initiation as the outcome and 6-month injection-risk behavior variables as the mediators. The lagged approach can be used as static measures at 6 months and 12 months, or changes in injection initiation social learning risks and IMB skills constructs that precede changes in the number of counts of initiation as outcome. This latter approach is strong in that the change in a variable, created by difference scores, is isolated so that it precedes the subsequent outcome.

There are also techniques for estimating mediational models with only 2 time-points;¹⁰⁹ consequently, we will examine mediation from randomization to 6-month follow-up with the mediator and outcome measured concurrently. We can estimate separate mediational models for each injection initiation social learning risk and IMB skills construct, or enter the mediation mechanisms together into a single model, while examining overfit due to multiple mediational paths.¹¹⁰ Omnibus measures of model fit (chi-square, root mean square error of approximation, Tucker Lewis Index [TLI]), and specific path coefficients will be used to assess the treatment effect and test for the mediational pathways. The null hypothesis will be rejected if the p value for the variable that denotes treatment condition is below 0.05. Proposed Co-I [name] has extensive experience with these techniques as part of longitudinal community-based interventions.^{105,111,112}

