13.2. Sample size/ power analyses

Power calculations were estimated using Mplus by creating a Monte Carlo Simulation by generating a synthetic data set based on the expected parameter values, such as slopes, standard errors, and correlations among measured variables, for the anticipated treatment effect.^{113,114} Power was estimated assuming an intracluster correlation of 0.5, which is similar to our previous NIDA-funded studies.^{105,112,115} Statistical tests were two-sided, allowing detection of effects in either direction, and an alpha of .05 and power at 80%, corresponding to moderate effect sizes. Because the outcome is a count (i.e., Poisson), standard errors were estimated as non-normal via a sandwich estimator in Mplus.¹¹⁶ Co-Is [name] and [name] found that the number of participants who initiated people into injection was halved at follow-up.⁷ Preliminary data from MPIs [name] and [name]'s study in LA and SF indicated that 809 active PWID were found to have initiated 431 people in the past year. Using the same proportion, we expect that 573 people would be initiated by our proposed sample size of 1,076 participants at baseline (286 in each arm). If the number of people initiated by intervention group participants is halved, as suggested by [name] and [name]'s pilot data, that would represent a reduction of 143 people not being initiated into injection.

We also calculated the effect under different assumptions of attrition, subgroups (e.g., 25% Latino), sex, and age. For brevity, we illustrate power for primary outcome and most conservative—changes in the number of injection initiation events. We also account for 25% attrition—our worst-case scenario. To test the three hypotheses given our alpha and power specifications, we would need a baseline recruitment of 1,076 (n=538 per condition). We will recruit 1,076 participants to achieve the final sample of approximately 800 at the 12-month data point. The sample power for Cohen's effect sizes for small (2 percentage point difference), medium (5% difference) and large (10%–15% difference) effect sizes are plotted in **Figure 4**, revealing that after

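### Whether treatment enters the baseline intercept of the H1/H2 model depends on the observed baseline comparison; one intercept specification should be fixed in advance

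*Combined protocol and SAP*

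**What the plan says.** The Aim 1 part of section 13.1 describes a two-part zero-inflated Poisson growth model over baseline, 6 and 12 months. Treatment acts on the slopes of the binary and count parts: "the model will include a treatment covariate representing the effect of the CTC intervention on changes over time".

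The intercept is handled conditionally: "if there are no differences at baseline in preliminary bivariate analyses, there is no need to include a treatment effect on the intercept". The reason given is that "the intercept test for difference is likely to be non-significant so there is no value in risking the extra degrees of freedom". No test, threshold or variable is named, and the text does not write out what happens when a difference is found.

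Other covariates are chosen in a similar way: "it may contain other covariates identified as having been distributed differentially by condition at baseline". The Aim 2 paragraph says that its model is estimated in the same manner, so the rule reaches H2 as well.

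Section 13.2 sets the error rate: "Statistical tests were two-sided, allowing detection of effects in either direction, and an alpha of .05 and power at 80"%. The only written rejection rule stands in the Aim 3 text: "The null hypothesis will be rejected if the p value for the variable that denotes treatment condition is below 0.05".

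Section 3.10 places randomisation after the baseline interview, and section 6.1 lists no stratification factors.

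**The concern.** Because participants are randomised after the baseline interview, any baseline difference in counts between arms is chance. The two branches of the rule nevertheless test different things.

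- **Common intercept.** Baseline means are held equal, and the slope test behaves like a baseline-adjusted comparison.
- **Intercept freed by arm.** The slope test becomes a comparison of change. The arm that started higher by chance tends to fall further through regression to the mean, and that fall is read as a treatment effect.

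The rule moves to the second estimator exactly when chance imbalance is largest. If CTC happened to enrol more high-volume initiators, part of their natural decline would count for CTC. If the control arm did, it would count against CTC.

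**Working it through.** **The plan's own figures.** The plan gives no error rate for this rule beyond alpha 0.05. Its attrition step reproduces approximately: 800 / 0.75 = 1,067 against the stated 1,076, and 1,076 × 0.75 = 807. The preliminary rate of 431 initiations by 809 people in a year is 0.533 per person-year, or about 0.266 per 6 months.

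**Assumptions not in the documents.** The baseline test is two-sided at 5%. The within-person correlation rho is 0.2 to 0.7. Section 13.2 uses an intracluster correlation of 0.5 but does not say that it is a correlation over time within a person.

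**Two time points, normal approximation, no true effect.** Let z0 and z1 be the standardised arm differences at baseline and follow-up, with correlation rho.

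- Adjusted test (common intercept): A = (z1 − rho·z0) / sqrt(1 − rho²). This is independent of z0, so it rejects 5% of the time at any imbalance.
- Change test (free intercept): T = (z1 − z0) / sqrt(2(1 − rho)). Given z0, T is normal with mean −z0·sqrt((1 − rho)/2) and variance (1 + rho)/2.

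Example: at rho = 0.5 and z0 = 1.96, T has mean −0.98 and SD 0.866. P(T < −1.96) is Φ(−0.98/0.866) = Φ(−1.13), about 0.13, nearly all of it in one direction.

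Averaging over |z0| > 1.96 gives the conditional rate. The rule as a whole rejects at 0.95 × 0.05 + 0.05 × (conditional rate).

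| rho | Change test, imbalanced trials | Common intercept, same trials | Whole rule |
|---|---|---|---|
| 0.2 | 0.273 | 0.05 | 0.0475 + 0.05 × 0.273 = 0.061 |
| 0.5 | 0.185 | 0.05 | 0.0475 + 0.05 × 0.185 = 0.057 |
| 0.7 | 0.130 | 0.05 | 0.0475 + 0.05 × 0.130 = 0.054 |

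**Three time points.** A linear growth model fitted by generalised least squares was run on 2,000,000 null trials per setting, with equal correlations. For rho 0.2, 0.5 and 0.7 the conditional rates are 0.275, 0.187 and 0.130, and the overall rates are 0.061, 0.057 and 0.054. The common intercept gives 0.050, 0.051 and 0.049 in the same imbalanced trials. Other correlation patterns (autoregressive, random slopes) give conditional rates from 0.11 to 0.31 and overall rates from 0.053 to 0.063.

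**Zero-heavy, overdispersed counts.** These used 400 per arm, 40,000 null trials per setting, and a least-squares test on log means.

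| Mean per 6 months | Free intercept, imbalanced trials | Whole rule | Common intercept always |
|---|---|---|---|
| 0.266 | 0.223 | 0.063 | 0.054 |
| 0.266 (more structural zeros) | 0.168 | 0.063 | 0.057 |
| 0.6 | 0.140 | 0.061 | 0.057 |

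The switch adds about 0.4 to 0.9 points here, on top of a small excess in the test itself.

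**Sensitivity to the trigger.** With a 10% baseline test the overall rate at rho 0.5 is 0.060. If the binary and count baselines were each tested at 5%, the switch could trigger in up to 1 − 0.95² = 9.75% of trials under independence.

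**The case against.** A reader might infer from the 13–27% that the trial as a whole runs at that error rate, or that the pre-test creates it. Neither follows. Those rates belong to any free-intercept change comparison looked at only in imbalanced trials. Used always, that comparison is valid: at rho 0.5 it gives 0.05 × 0.185 + 0.95 × 0.043 = 0.050. The switch keeps the excess in imbalanced trials and drops the offset in the others, and that costs 0.4 to 1.1 points.

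A reader might also infer a bias towards CTC. Under the null the two directions are equally likely. By symmetry, false claims for CTC rise from 2.5% to about 2.7–3.05%.

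Nor do the documents state a 5% significance test, or say that the arm path is added when a difference appears. Both are inferred from the conditional wording and from its appeal to non-significance. If that inference is refused, the primary model is simply undefined when imbalance occurs, which also needs a sentence.

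Section 13.1 has partial safeguards: analysts are blinded to which code is CTC, contrasts within time points are planned, and the rate-of-change result will be compared with differences at each follow-up. These limit steering by preference and make a fragile result more visible. They do not remove the rule, because its effect comes from the observed imbalance and not from the analyst's wishes.

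The strongest remaining point is that no calculation here fits the planned Mplus model. That stands. It affects the percentages more than the mechanism.

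**Conclusion.** The point holds as a minor one. The intercept specification for H1 and H2 is left to the observed baseline comparison, and the implied switch raises the overall two-sided type I error from 5% to about 5.4–6.1%. The practical weight lies in the conditional result. If this one trial shows a significant baseline imbalance (about 1 chance in 20), the free-intercept slope test would reject a true null 13–27% of the time, in the direction set by which arm started higher, where a common intercept would keep 5%.

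This rests on an assumed 5% baseline test, an assumed correlation of 0.2 to 0.7, the inferred second branch, and normal and log-mean analogues of the two-part model.

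**What to change.** Remove the baseline comparison as a model selector. State one model for H1 and H2, to be used whatever imbalance is observed: treatment acts on the binary and count slopes, with no arm effect on either intercept and with the intercept-slope covariances freely estimated. The covariances matter because a common intercept works like baseline adjustment only if the link between baseline and follow-up is modelled properly.

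As an alternative, pre-specify adjustment for the baseline count, with the 6- and 12-month counts as outcomes. In a two-part count model this is a different model, not an identical one, so the SAP should name one of the two as primary. Baseline tables can stay as description.

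The cost is two or three sentences and no extra data or participants. Section 13.1 itself raises identification with three time points, so the team should check on simulated data, before unblinding, that the chosen model with free covariances converges.

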2.0 OBJECTIVES AND PURPOSE

To achieve these aims, people who inject drugs (PWID) who report having initiated someone or having injection initiation social learning risks in the past 6 months (N=1,076) will be randomly assigned to receive CTC or an equal attention control condition in Los Angeles (LA) and San Francisco (SF), CA. Injection initiation

and injection initiation social learning variables will be collected at baseline, 6 months, and 12 months. CTC is brief, easy to implement, and novel in its focus on active PWID as a conduit for preventing injection initiation. If proven efficacious, CTC will be a much-needed, practical approach to preventing drug injection initiation.³⁹⁻⁴³

The main outcomes by Aim are as follows: 1) Counts of non-injectors initiated into drug injection at 6 and 12 months; 2) Counts of request to initiate a non-injector into drug injection at 6 and 12 months; and 3) Counts of noninjectors initiated into drug injection and request to initiate non-injectors at 6 and 12 months. The study will be implemented in 2 phases. Phase 1 involves adaptation and training of intervention personnel and Phase 2 involves implementing the full study.

Elucidation goals are to better understand issues related to 1) HAV/HCV effects and 2) drug effects and withdrawal and symptoms management PWID.

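### The supplementary by-visit comparison of 6- and 12-month counts mentions no baseline count, so it is less precise than it need be and a disagreement with the latent change model would be hard to read

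*Combined protocol and SAP*

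**What the plan says.** Section 13.1 (Aim 1) tests H1 with a two-part zero-inflated Poisson latent growth model fitted to baseline (T0), 6 months (T1) and 12 months (T2). The baseline count is therefore part of the main analysis. By-visit contrasts at T1 and T2 are also planned inside that model, through constraints. A treatment effect on the intercept is left out if preliminary analyses show no baseline difference.

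At the end of the Aim 1 text comes a separate check: "we will compare differences in examining the rate of change versus the standardized difference at each follow-up point". The plan gives comparing the 6- and 12-month counts as its example, with a test by condition. It adds that "The latent change model has more power than the raw difference approach", and says that differences will be published if the result depends on how the model is estimated. No baseline term is mentioned in this check.

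The baseline value exists. Section 2.0 says that injection initiation "and injection initiation social learning variables will be collected at baseline, 6 months, and 12 months", and section 3.19 repeats the main outcome items of section 3.16 at both follow-ups.

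The only correlation stated is in section 13.2: "Power was estimated assuming an intracluster correlation of 0.5". The unit of clustering is not named.

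**The concern.** A count of initiations over the past 6 months is likely to depend on the person. Under section 2.0, people enter either because they initiated someone recently or only because of a social-learning risk, so baseline counts will vary and should predict later ones. A by-visit comparison that ignores them carries variance that could be removed at almost no cost.

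The plan treats the lower power of the raw approach as a property of the method. Part of it comes from leaving out the baseline count.

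What is at stake is how the check is read. The latent model uses baseline and the check, as written, does not. If they differ, readers cannot tell whether the growth-model assumptions matter, whether the arms differed by chance at baseline, or whether the check was simply less precise. The plan would put any of these down to model estimation.

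**Working it through.** **Inputs from section 13.2.** "Statistical tests were two-sided, allowing detection of effects in either direction"; "an alpha of .05 and power at 80%, corresponding to moderate effect sizes"; "we would need a baseline recruitment of 1,076 (n=538 per condition"); "We also account for 25% attrition"; about 800 participants at 12 months (400 per arm); 431 people initiated by 809 people who inject drugs in a year; counts halved in the intervention arm.

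**The plan's own figures.** 1,076 × 431/809 = 573, or about 286 per arm, and halving removes 143. 1,076 × 0.75 = 807, or about 800. All match. The stated powers of 0.82, 0.88 and 0.99 come from a simulation whose parameters are not given. They could not be reproduced, and they are not stated to be powers for the by-visit comparison.

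**Assumptions.** The baseline-to-follow-up correlation r and the unadjusted power of this comparison are not in the documents. Below, r is varied and 80% is used as an illustrative starting power.

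**Step 1: variance.** Relative to a post-only comparison (1.00), adjusting for baseline gives 1 − r² and a change score gives 2(1 − r). At r = 0.5 these are 0.75 and 1.00. The ratio of the first to the second is (1 + r)/2, so adjustment is never worse than a change score.

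**Step 2: power.** Adjusted power = Φ[(1.96 + 0.8416)/√(1 − r²) − 1.96].

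| r | Adjusted power, from 80% | Gain (points) |
|---|---|---|
| 0.2 | 81.6% | 1.6 |
| 0.3 | 83.6% | 3.6 |
| 0.4 | 86.4% | 6.4 |
| 0.5 | 89.9% | 9.9 |

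The gain shrinks as the starting power rises. At r = 0.5, 0.88 becomes 0.952 and 0.99 becomes 0.999.

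**Step 3: the plan's event rate.** The 6-month mean is 431/809/2 = 0.266 if the rate is constant (assumed). For a halved count with 400 per arm and dispersion φ, z = 0.133/√(φ × 0.3996/400). With r = 0.5, unadjusted against adjusted power is 0.988 v 0.998 (φ = 1), 0.846 v 0.931 (φ = 2) and 0.682 v 0.802 (φ = 3). The gain is 1 to 12 points, depending on a dispersion that the plan does not give.

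**Step 4: simulated counts.** A gamma person effect (shape k, assumed) is shared by baseline and follow-up, with 400 per arm and mean 0.266. The linear model had 3,000 runs. The Poisson model, with baseline as any/none plus log(1 + count), had 1,500. Both used robust standard errors.

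| Rate ratio | k | r | Model | Unadjusted | Adjusted |
|---|---|---|---|---|---|
| 0.5 | 0.3 | 0.47 | Poisson | 0.915 | 0.947 |
| 0.5 | 0.3 | 0.47 | linear | 0.915 | 0.959 |
| 0.5 | 0.2 | 0.56 | linear | 0.860 | 0.950 |
| 0.5 | 0.15 | 0.63 | Poisson | 0.787 | 0.931 |
| 0.6 | 0.3 | 0.47 | linear | 0.697 | 0.790 |
| 0.6 | 1 | 0.21 | linear | 0.838 | 0.853 |

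Only the rate ratio of 0.5 is the plan's. The person effect is assumed fully stable over time; if it fades, r and the gain are smaller.

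**Step 5: against the growth model.** With three visits, equal correlations of 0.5, and variance in units of SD²/n per arm, the 12-month effect has variance 2.00 post-only and 1.50 baseline-adjusted. The growth slope has 1.45 without a treatment effect on the intercept and 2.00 with one. Adjustment therefore recovers most of the latent model's advantage in the first case. In the second, the raw comparison is no less precise than the slope, and the adjusted one is more precise than both.

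**The case against.** The strongest reply is that this is a supplementary check. H1 is tested by the latent model, which contains T0, and T1 and T2 contrasts are already planned inside it. The plan also discloses the lower power and promises to show differences. All of this stands, and it limits the point. It does not remove it, because the contrasts inside the latent model share its assumptions and cannot serve as a separate check on them.

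The text does not expressly exclude baseline either. It moves from a standardized to a raw difference without defining either, and the raw difference might be an observed change score. That is a fair reading, but step 1 shows that a change score is no more precise than a post-only comparison at r = 0.5 and less precise below it, so the case for adjustment remains.

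A reader might infer three stronger points that the documents do not support:

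- *That the check is a poor one.* Under randomisation the unadjusted difference is unbiased, and it avoids the growth-model assumptions. It is valid but less precise.
- *That the trial loses 10 points of power.* That figure needs r = 0.5 and an unadjusted power near 80%. The 0.5 in section 13.2 is an intracluster correlation and is not identified as the correlation between baseline and follow-up counts.
- *That H2 is equally affected.* The Aim 2 text says that the model is estimated in the same way. Whether the by-visit comparison is repeated there is not stated.

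**Conclusion.** The point holds as a modest gain in precision and in interpretability for a supplementary analysis. It does not touch the validity of the main H1 test.

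Its size cannot be fixed from the documents. From an assumed 80%, the gain is under 4 points for r up to 0.3 and about 10 at 0.5. Under the plan's halving with r near 0.47, the simulations give 3 to 4 points because unadjusted power is already about 0.92. Gains are larger if the counts are more dispersed and more strongly correlated, and about 1 point where power is already 0.99. The assumptions are r, the dispersion, a constant event rate and the starting power.

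**What to change.** In section 13.1, state that the by-visit comparison is a regression of the 6-month and 12-month counts on arm, with robust standard errors, that always includes the participant's baseline value of the same count, whatever any baseline test shows. Prespecify the form of the baseline term; any versus none plus log(1 + count) is one reasonable choice. Apply the same to the Aim 2 count if the comparison is made there.

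Set the adjusted rate ratios and confidence intervals, rather than p-values, against the latent change model, and still report the unadjusted difference beside them. The same sentence should replace the undefined mix of standardized and raw difference.

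No new data, visits or participants are needed. The cost is one or two degrees of freedom and the need to choose the baseline term in advance.
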